### 13.2 Trial analysis sets

All subjects enrolled in the trial (i.e. subjects for whom informed consent has been obtained and who have been registered in the trial) will be accounted for in the clinical trial report.

All subjects randomised are included in the full analysis set (FAS) and will be used for efficacy analyses. Exclusions from the FAS can be considered in special cases as described in ICH E9, Section 5.2.1. If it is decided to exclude a randomised subject from the FAS, a justification addressing ICH E9 will be given. Subjects contribute to the evaluation ‘as randomised’.

A safety analysis (SAS) set will be defined as subjects receiving treatment with IMP. The decisions regarding inclusion/exclusion of subjects and/or subject data from the trial analysis sets will be documented in the statistical analysis plan update before breaking the

randomisation code/clinical trial report. Subjects in the safety analysis set contribute to the evaluation 'as treated'.

### **13.3 Statistical analysis**

#### **13.3.1 Disposition of subjects**

A subject disposition will be made including information of number of subjects screened, randomised, exposed, completing and withdrawn (and reason for withdrawal), by treatment group and in total. This will also include number of subjects included in the FAS and safety analysis set, by treatment group and in total.

#### **13.3.2 Demographics and other baseline characteristics**

Descriptive statistics of demographics and other baseline characteristics will be presented for all randomised subjects by treatment group. Presentations of age, sex, ethnicity, race, and baseline efficacy assessment by treatment will also be given by centre.

Demographics include age, sex, race, and ethnicity. Other baseline characteristics include vital signs (including height, weight, BMI), duration of psoriasis, concurrent diagnoses (from medical history and indications for concomitant medication), concomitant medication, and previous anti-psoriatic therapy.

#### **13.3.3 Exposure and treatment compliance**

Relevant exposure, compliance and drug accountability data will be tabulated.

#### **13.3.4 Endpoints**

In support of the objectives stated in [Panel 3](#), the endpoints of the trial are prioritised as follows:

##### **Co-primary endpoints:**

- At least 75% improvement from baseline at Week 24 in Psoriasis Area and Severity Index (PASI)
- Static Physician's Global Assessment (sPGA) scale score of 0 or 1 at Week 24

##### **Secondary endpoints:**

- At least 90% improvement from baseline at Week 24 in PASI
- 100% improvement from baseline at Week 24 in PASI
- Change from baseline at Week 24 in PASI score

- PASI improvement (%) from baseline at Week 24
- Change from baseline at Week 24 in affected body surface area (BSA)
- Psoriasis Symptom Inventory (PSI) responder at Week 24 (total score  $\leq 8$ , with no item scores  $> 1$ )
- PSI total score of 0 at Week 24
- Number of symptom-free days from randomisation to Week 24 (symptom-free day = daily total PSI of 0 on that day)
- Burden of symptoms assessed as the normalised area under the curve (AUC) of PSI from baseline to the last available assessment
- Change from baseline at Week 24 in Dermatology Life Quality Index (DLQI) total score
- DLQI total score of 0 or 1 at Week 24
- Frequency of AEs and SAEs by preferred term

**Other endpoints:**

- Change from baseline at Week 24 in Nail Psoriasis Severity Index (NAPSI) total score

### 13.3.5 Analysis of primary endpoint

The co-primary endpoints PASI 75 and sPGA (0 or 1) at Week 24 (end of treatment visit) will be evaluated on the FAS.

Estimates and 95% confidence intervals (CI) for the response rates and treatment differences will be presented. The differences in response rates between treatment groups will be analysed using the Cochran-Mantel-Haenszel test with stratification by weight group ( $\geq 100$  kg or  $< 100$  kg). The null hypotheses of no difference in response rates between brodalumab and fumaric acid esters will be tested against the two-sided alternative that there is a difference on a 5% level. Subjects who drop-out of the trial before Week 24 (end of treatment visit) will be regarded as non-responders. A sensitivity analysis will be made where ineligible subjects randomised in error into the trial are excluded from the analysis.

As supportive analyses for the co-primary endpoints, a logistic regression model with baseline PASI or sPGA and weight group will be performed, and further, the mixed model for repeated measurements (MMRM) for PASI described below will be used to predict PASI 75 for subjects without assessments at Week 24 for an additional Cochran-Mantel-Haenszel analysis. Finally, subjects who drop-out of the trial before Week 24 will be LOCF imputed and analysed using the Cochran-Mantel-Haenszel test.

The trial is considered a success if superiority is confirmed for both primary endpoints.

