#### Fumaric acid esters efficacy:

The response rate for fumaric acid esters is expected to be lower than for brodalumab. In a systemic review, the rate is reported to be on par with methotrexate (Smith 2017).

Methotrexate (MTX) for 24 weeks is reported to achieve at least PASI 75 in 51% of patients (Mrowietz and Warren et al. 2017).

In the European Consensus, fumaric acid esters and MTX are considered slow-acting drugs and the endpoint should therefore be measured between Week 16 and Week 24 (Mrowietz and Szepietowski et al. 2017). In most reports on fumaric acid esters, clinical effects are from open studies and only few studies have been performed using evidence based criteria (Nast et al. 2012). For fumaric acid esters, the S3 guideline estimates a PASI 75 in 50 to 70% of patients at Week 16 (Nast et al. 2012). However, in a trial comparing fumarates versus MTX, only 39% of evaluable patients in the fumarates group had a  $\geq 75\%$  reduction in PASI at Week 20 (the rate was 32% in the MTX group) (Fallah Arani et al. 2011).

In an observational study, mean PASI scores were reduced from 19.84 to 7.35 after 12 months (63% improvement) (Walker et al. 2014), and it was noted that several multi-centre trials had demonstrated the efficacy of fumaric acid esters in psoriasis with a PASI 75 in about 50% of patients.

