## 13 Statistical methods

### 13.1 Sample size

The effect on psoriasis symptoms of subcutaneous injections of brodalumab will be compared to oral administration of fumaric acid esters in subjects with moderate to severe plaque psoriasis who are naïve to systemic treatment.

Formally, this will be formulated by testing the null hypotheses of equality of proportion of PASI 75 response and sPGA (0 or 1) success to treatment with brodalumab compared with treatment with fumaric acid esters; against the alternative hypothesis that the two proportions differ.

The sample size is determined using Fisher's exact test for the two independent proportions under the assumption of a two-sided test of size 5%. Based on experience from previous trials with brodalumab and fumaric acid esters in subjects with moderate to severe psoriasis, conservative estimates for the proportion of PASI 75 responders of 80% for brodalumab and between 50% and 70% for fumaric acid esters ([Nast et al. 2012](#)) are used in the sample size calculation (using Proc Power in SAS version 9.4). Assuming a dropout rate of 50% for

fumaric acid esters, a PASI 75 response rate combined with NRI will correspond to a total rate of responders of 25%. A dropout rate of less than 40% with brodalumab, a PASI 75 response rate will correspond to a total rate of responders of 48%.

For sPGA, the expected rate of sPGA success is 37.4% with fumaric acid esters ([Mrowietz and Szepietowski et al. 2017](#)), while varying rates above 60% has been seen in the previous brodalumab trials.

An overview of the estimated power within the given spread of response rates, is presented in [Panel 13](#).

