### **13.3.6 Analysis of secondary efficacy endpoints**

All binary endpoints will be analysed in a similar manner as the co-primary endpoints, by analysing the difference in response rates between treatment groups using the Cochran-Mantel-Haenszel test.

Continuous endpoints like absolute PASI score, % PASI improvement, and NAPSI improvement will be modelled by MMRM to compare treatments through Week 24. The mixed model will include treatment group, week, interaction between treatment and time, baseline PASI/NAPSI score, and baseline weight group as fixed factors. Within subject covariance will be estimated by an unstructured covariance matrix (if possible).

Number of symptom-free days will be summarised.

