### **13.3.10 General principles**

All statistical analyses of efficacy endpoints will be based on the FAS and safety endpoints on the safety analysis set (SAS). All significance tests will be two-sided using the 5% significance level. All CIs will be presented with 95% degree of confidence. No corrections for multiplicity will be performed.

If not mentioned otherwise, endpoints will be summarised descriptively at each visit by treatment and in total.

An observed-cases approach will be used for tabulations of data by visit (i.e. involving only those subjects who attended each specific visit). For categorical endpoints number of subjects not attending each specific visit will also be added.

Categorical data will be summarised using the number and percentage of subjects in each category. Continuous data will be summarised using the mean, median, SD, minimum, and maximum values.

In general, for endpoints evaluated as change from baseline and/or where a baseline adjustment is applied, baseline is defined as information collected at the randomisation visit (Visit 2), if not otherwise stated. If the assessment is not available at the randomisation visit but at the screening visit (Visit 1) then this will be used instead.

All the analyses specified in the protocol will be reviewed in relation to the blinded data obtained and the statistical analysis plan update will be finalised before breaking the randomisation code.

Any changes from the statistical analysis planned in this clinical trial protocol will be described and justified in the statistical analysis plan update (SAPU) and/or in the clinical trial report dependent on the type of deviation.

For endpoints evaluated over time, plots will be made to explore the trajectory with time.

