### **13.3.11 Handling of missing values**

Missing data for categorical endpoints will be imputed with non-responder imputation. Missing data for continuous endpoints will be dealt with by a mixed model for repeated measurements.

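### The supportive PASI 75 analysis appears to treat MMRM-predicted responses as observed data, so its p-value and interval would be too optimistic

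*Combined protocol and SAP*

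**What the plan says.** The primary analysis of each co-primary endpoint is a Cochran-Mantel-Haenszel (CMH) test stratified by weight group, with dropouts counted as non-responders (Section 13.3.5).

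Among the supportive analyses, the PASI mixed model (MMRM) "will be used to predict PASI 75 for subjects without assessments at Week 24 for an additional Cochran-Mantel-Haenszel analysis". The Protocol summary repeats this. A further supportive analysis covers dropouts by last observation carried forward: "subjects who drop-out of the trial before Week 24 will be LOCF imputed and analysed using the Cochran-Mantel-Haenszel test".

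The model itself is described in Section 13.3.6: "Continuous endpoints like absolute PASI score, % PASI improvement, and NAPSI improvement will be modelled by MMRM to compare treatments through Week 24". That section gives the fixed effects and the covariance structure only. It does not say which of the two PASI models (absolute score or % improvement) feeds the prediction, or how a predicted value becomes a responder status.

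Section 13.3.11 sets non-responder imputation for categorical endpoints and adds "Missing data for continuous endpoints will be dealt with by a mixed model for repeated measurements". Section 13.3.10 offers "An observed-cases approach will be used for tabulations of data by visit" and provides for a plan update finalised before the code is broken. None of these sections mentions draws, a number of imputations, pooling or a bootstrap.

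**The concern.** On the natural reading, each subject without a Week 24 PASI gets one model-predicted status, and a single CMH test then treats all 204 statuses as data. Two errors follow.

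- **Uncertainty is understated.** The predictions share the same estimated model coefficients, so predicted statuses near the 75% cut flip together from one trial to the next. The CMH variance counts them as independent observations.
- **Response rates are pushed away from the cut.** A conditional mean varies less than a real outcome. A group whose mean lies above 75% improvement gets too many predicted responders, and a group below it too few.

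This is the plan's only model-based treatment of missing PASI 75 status. Readers will set it beside the non-responder result to see whether superiority depends on counting dropouts as failures. If its precision is overstated, and its difference too large in some settings, it can reassure falsely.

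The MMRM comparisons of continuous PASI are not affected; they remain valid under missing at random.

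**Working it through.** **Plan figures reproduced.** The plan states no operating characteristics for this analysis. Section 13.1 does give the rates behind it:
- Fumarate: 0.50 × (1 − 0.50) = 25%, as stated.
- Brodalumab: 0.80 × (1 − 0.40) = 48%, as stated. So 40% is the working value, although the text calls it an upper bound.

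**Share of outcomes predicted (102 per arm).**

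| Dropout (brodalumab/fumarate) | Predicted | Share of 204 |
|---|---|---|
| 40%/50% | 41 + 51 = 92 | 45% |
| 20%/50% | 20 + 51 = 71 | 35% |
| 20%/20% | 0.20 × 204 = 41 | 20% |

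**Why thresholding shifts the rate.** Take normally distributed improvement, random dropout, and correlation r between the last attended visit and Week 24. If the true rate is p, the predicted rate among dropouts is Φ(Φ⁻¹(p)/r). With dropout d, the analysed rate is (1 − d)p + d·Φ(Φ⁻¹(p)/r). Take r = 0.69:
- Brodalumab, p = 80%, d = 40%: Φ(0.842/0.69) = 88.9%, so the analysed rate is 0.6 × 80 + 0.4 × 88.9 = 83.5%.
- Fumarate, p = 50%, d = 50%: unchanged at 50%. The difference is 33.5 points against a true 30.
- Fumarate, p = 39%: Φ(−0.279/0.69) = 34.3%, so the analysed rate is 36.6%. The difference is 46.9 points against 41.
- Fumarate, p = 70%: Φ(0.524/0.69) = 77.6%, so the analysed rate is 73.8%. The difference is 9.7 points against 10.

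**Simulation set-up.** Dropout rates and response rates come from the documents; everything else is assumed.
- Visits at Weeks 1, 2, 3, 4, 6, 8, 12, 16, 20 and 24; 30% of subjects at or above 100 kg.
- % improvement with SD 25, capped at 100. Mean curves are exponential: 0.15 per week under the null; 0.35 (brodalumab) and 0.12 (fumarate) under the alternative.
- Adjacent-visit correlation 0.80, 0.91 or 0.97. Week 8 to Week 24 is four steps, giving 0.41, 0.69 or 0.89.
- Last visit attended spread over Weeks 1–20, early (1–4) or late (8–20). Dropout is random or logistic in current response (slope 1 per SD).
- Prediction is the conditional mean given earlier visits, arm and weight group. Baseline PASI was not simulated, so it is left out.
- 4 rates × 3 correlations × 3 timings × 2 mechanisms = 72 scenarios per dropout level. Runs per scenario: 1000 null trials, 400 alternative trials (40%/50% only). Monte Carlo error is about ±2 points at 14%.

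**Type I error, equal arms, true rate 39–70%, nominal 5%.**

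| Dropout | Median |
|---|---|
| Complete data | 5% (range 3–7%) |
| 20%/20% | 7% (range 4–23%) |
| 20%/50% | 14% |
| 40%/50% | 14% |

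At 40%/50% with late or spread dropout, the range is 6–33% (median 12%). When all dropout falls in Weeks 1–4, it reaches 46%. By Week 8–24 correlation 0.41, 0.69 and 0.89, the medians are 20%, 15% and 9%.

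**True SD of the difference divided by the reported standard error.** 40%/50%: 1.03–2.85 (median 1.34). 20%/20%: 1.01–1.67 (median 1.11).

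**Bias in the difference, brodalumab 80%, dropout 40%/50%.**

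| Fumarate rate | Range (points) | Median |
|---|---|---|
| 39% | +2 to +23 | +9 |
| 50% | +2 to +19 | +6 |
| 60% | +1 to +7 | +3 |
| 70% | −4 to +4 | 0 |

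The planning range in Section 13.1 is "between 50% and 70% for fumaric acid esters". The 39% lies below it: Section 6.2.2 reports "only 39% of evaluable patients in the fumarates group" reaching the threshold at Week 20.

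**Second, simpler simulation.** One stratum, one earlier visit, dropout dependent on that visit, 3000 trials per scenario. At 40%/50% dropout and null rates of 50–65%, type I error was 22.8–26.7% at correlation 0.5 and 9.5–10.8% at 0.8. At a 65% null rate, the true SD was 0.110 against a reported 0.064 (ratio 1.7), and 0.081 against 0.066 (ratio 1.2). At 80% v 50%, the difference rose from 0.30 to 0.42 and 0.35. At 10% dropout in each arm, type I error was 5.6–7.9%.

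**Multiple imputation.** In the main simulation at 40%/50% (20 imputations; 400 null and 150 alternative trials per scenario), type I error was 1–6% (median 3%). Bias was within 3 points (median 0.3 or less). The simpler simulation gave a type I error of 0.8–4.5% across its scenarios.

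**The case against.** - **The defect is inferred.** The text does not say how the prediction is made, and the plan update may specify draws. This stands: the conclusion is conditional on the natural reading. But if draws were intended, everything needed to run them is still missing.
- **No decision rests on it.** Success depends only on the two primary CMH tests. This also stands. The type I error here measures how misleading the supportive p-value can be; it is not an error rate of the trial. The supportive sentence does not itself promise a confidence interval.
- **The supportive conclusion may seldom change.** Using SE = √[(0.8 × 0.2 + p(1 − p))/102] for fumarate rate p, z at 80% v 50% is 0.30/0.0634 = 4.7, and 3.5 after dividing by 1.34 (p = 0.0004). At 80% v 60%, z falls from 3.2 to 2.4 (p = 0.017). At 80% v 70% it is not significant either way (1.7, 1.2). This is fair for a typical case, and it limits the severity. With the extreme ratio of 2.85, significance is lost at 50% and at 60% (z = 1.7 and 1.1).
- **The sizes rest on assumptions.** The 46% needs early, response-dependent dropout and adjacent-visit correlation 0.80, so that the last attended visit correlates only 0.13–0.26 with Week 24. The planned model includes baseline PASI; the simulation does not. The 40% for brodalumab is a bound and the 50% for fumarate an assumption, so 92 is a planning figure and no guaranteed maximum. All of this stands. It affects the size; the direction held in both simulations.

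**Conclusion.** The concern holds. As written, and on its natural reading, the supportive PASI 75 analysis understates uncertainty. At 40%/50% dropout the median type I error is 14% against a nominal 5%, and the median ratio of true SD to reported standard error is 1.34. At 20% dropout in each arm the medians are 7% and 1.11.

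The estimated difference is clearly too large only if fumarate response is about 39–50%. It is small at 60% and has no consistent sign at 70%. The 46% is a worst case and should not be read as typical.

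These sizes depend on assumed correlation, dropout timing and mechanism. The primary analysis, the sample size and the success rule are untouched. The change should be made, with medium confidence in the exact magnitude.

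**What to change.** In the statistical analysis plan update, before the code is broken, replace the single prediction by multiple imputation:

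1. Name the PASI model used (absolute score or % improvement).
2. Draw missing Week 24 PASI values from it, including parameter uncertainty; state the number of imputations and the seed.
3. Apply the 75% threshold in each completed data set.
4. Run the weight-stratified CMH test and risk difference in each, and combine by Rubin's rules.
5. State that the analysis estimates response had subjects stayed, under missing at random, which is a different question from non-responder imputation.

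An optional addition is a matching multiple imputation for sPGA, using the scores already scheduled at every visit from baseline. For sPGA, carrying the last observation forward is the only inferential alternative to non-responder imputation. The correction for PASI 75 does not depend on this.

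The cost is plan-update wording and modest programming, with no new data. Intervals for the supportive analysis will be wider. Rubin pooling was slightly conservative in the simulations, and the result still rests on the untestable missing-at-random assumption.

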### **13.3.6 Analysis of secondary efficacy endpoints**

All binary endpoints will be analysed in a similar manner as the co-primary endpoints, by analysing the difference in response rates between treatment groups using the Cochran-Mantel-Haenszel test.

Continuous endpoints like absolute PASI score, % PASI improvement, and NAPSI improvement will be modelled by MMRM to compare treatments through Week 24. The mixed model will include treatment group, week, interaction between treatment and time, baseline PASI/NAPSI score, and baseline weight group as fixed factors. Within subject covariance will be estimated by an unstructured covariance matrix (if possible).

Number of symptom-free days will be summarised.

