### **13.3.7 Analysis of patient reported outcomes**

The PROs will be summarised by treatment and stratification group. Further DLQI, change from baseline will be compared between treatments by MMRM including treatment group, week, interaction between treatment and time, baseline DLQI score and baseline weight group as fixed factors. Within subject covariance will be estimated by an unstructured covariance matrix (if possible). DLQI total score of 0 or 1 will be analysed by a Cochran-Mantel-Haenszel model adjusting for baseline weight group.

The AUC for the PSI total score will be calculated for each subject using the standard trapezoidal rule. The AUC will be normalised by dividing with the time period from baseline to the last available assessment of the PSI total score. The normalisation converts the AUC to the original scale of the PSI total score. Missing assessments of the PSI total score in-between non-missing assessments will not be imputed, which corresponds to linear interpolation between the non-missing assessments of the PSI total score. The normalised AUCs will be analysed using an analysis of covariance (ANCOVA) with treatment group, baseline weight group and the baseline PSI total score as explanatory variables.

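### The MMRM for PASI applies one baseline slope at every visit; this can cost precision for the Week 24 PASI score and change, and a baseline-by-week term guards against that at almost no cost

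*Combined protocol and SAP*

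**What the plan says.** Section 13.3.6 models absolute PASI, percentage PASI improvement and NAPSI by MMRM with an unstructured covariance where that can be fitted. The fixed effects are listed in full: "The mixed model will include treatment group, week, interaction between treatment and time, baseline PASI/NAPSI score, and baseline weight group as fixed factors". Section 13.3.7 uses the same form for DLQI, "by MMRM including treatment group, week, interaction between treatment and time, baseline DLQI score and baseline weight group as fixed factors". No other section adds an interaction of baseline with week.

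Panel 2 schedules PASI at Weeks 1, 2, 3, 4, 6, 8, 12, 16, 20 and 24, which is ten post-baseline visits. Section 13.3.4 lists "Change from baseline at Week 24 in PASI score" as a secondary endpoint. The PASI model has a second use in Section 13.3.5, where the "mixed model for repeated measurements (MMRM) for PASI described below will be used to predict PASI 75 for subjects without assessments at Week 24" in a supportive analysis of a co-primary endpoint. Section 13.3.11 relies on the MMRM for missing continuous data.

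**The concern.** One week into treatment a subject's PASI should still lie near its baseline value. By Week 24, Section 13.1 expects at least 75% improvement in 80% of brodalumab subjects and in 50% to 70% of fumaric acid ester subjects, before dropout is counted. What remains is then a small part of baseline, and the slope on baseline should be much flatter.

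A single slope fitted by maximum likelihood is a weighted compromise. The early visits, with less residual variance, can pull it towards their own steep slope. If it is wrong for Week 24, baseline variation that should have been removed stays in the contrast, and a chance baseline imbalance between arms is over-corrected or under-corrected. Precision of a named secondary endpoint is at stake. So is the PASI 75 prediction for dropouts, if the absolute-PASI model is the one used there. Change from baseline is affected exactly as the score is: subtracting baseline lowers every slope by 1, the fitted common slope included, so the adjusted Week 24 contrast is the same number.

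**Working it through.** **The plan's own figures.** The documents give power only for the binary endpoints. With 102 per arm, the arcsine approximation to Fisher's test with continuity correction gives 0.9103 for 25% against 48% and 0.8757 for 37.4% against 60%. Their product is 0.797, which matches Panel 13 (0.910, 0.876, 80%). No SD, power or precision is stated for the PASI MMRM.

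**Formula, complete data.** Let b be the vector of true baseline slopes by visit, S the residual covariance, s24 the Week 24 residual SD, B baseline PASI and n the number per arm.

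- Common slope: bc = (1'S⁻¹b) / (1'S⁻¹1)
- Planned model: Var = (2/n)[s24² + (b24 − bc)² Var(B)]
- Slopes by week: Var = (2/n) s24²
- SE ratio: √[1 + (b24 − bc)² Var(B) / s24²]

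**Inputs.** From the documents: n = 102, ten visits, baseline PASI above 10. Assumed:

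- baseline mean 19.6 and variance 57.6 (SD 7.6)
- slope 0.9 at Week 1, decaying towards a late value L as L + (0.9 − L)exp[−(w − 1)/5]
- residual SD 3 at Week 1, rising towards s as 3 + (s − 3)(1 − exp[−(w − 1)/4])
- correlation 0.6 to the power |√w − √w′|

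**One case in full (L = 0.2, s = 6).** At Week 24 the slope is 0.207 and the residual SD 5.99. The common slope comes to bc = 0.776. The added variance is (0.207 − 0.776)² × 57.6 = 18.6 against 5.99² = 35.9, so the ratio is √(1 + 18.6/35.9) = 1.23. That equals losing 1 − 1/1.23² = 34% of the sample. A 1-point baseline imbalance moves the estimate by 0.207 − 0.776 = −0.57 points. With no baseline adjustment of the Week 24 score, the ratio is √(1 + 0.207² × 57.6/35.9) = 1.03, so here the planned adjustment is worse than none.

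**SE ratio, planned model to slopes by week:**

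| Late slope L | s = 4 | s = 6 | s = 8 |
|---|---|---|---|
| 0.9 (constant) | 1.000 | 1.000 | 1.000 |
| 0.6 | 1.052 | 1.047 | 1.035 |
| 0.4 | 1.140 | 1.125 | 1.094 |
| 0.2 | 1.259 | 1.232 | 1.178 |
| 0 | 1.403 | 1.363 | 1.281 |

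With adjacent-visit correlation 0.7 or 0.85 instead, baseline SD 5 or 7.6 and s = 6, the ratio is 1.02–1.05 for L = 0.6, 1.04–1.15 for 0.4 and 1.08–1.27 for 0.2.

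**Simulated fits** (maximum likelihood, unstructured covariance, 400 trials per scenario, s = 6). For L = 0.4, 0.2 and 0 the model-based SE ratios were 1.13, 1.24 and 1.37 with complete data. With missing-at-random dropout leaving 46% and 63% completers they were 1.11, 1.21 and 1.33. A multiplicative model (PASI as baseline times a remaining fraction) gave 1.06–1.10 complete and 1.13–1.22 with dropout. With a constant slope the extra term cost nothing measurable: SE ratio 1.000, empirical SD ratio 0.996–1.002.

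**Wider grid, proportional improvement** (baseline mean 16–20, SD 5–8; ratio of the SD of the Week 24 difference, complete data):

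- *No baseline rating error, subject differences in response growing over time (48 settings):* 1.06–1.61, median 1.19. Fitted common slope 0.57–0.91 against 0.24–0.28 at Week 24. A 1-point imbalance moves the planned estimate by −0.31 to −0.65, and the by-week estimate by at most 0.07.
- *With baseline rating error (108 settings):* 1.00–1.25, median 1.01, above 1.05 in 23. The 72 settings with subject differences already present at Week 1 give 1.00–1.03. A 1-point imbalance moves the planned estimate by −0.51 to +0.16.
- *All 156 settings:* the planned model beats unadjusted change every time (ratio 0.45–0.97), but is worse than the unadjusted Week 24 score in 78 (ratio 0.90–1.42).
- *With random dropout of 40% and 50%:* 0.97–1.51, median 1.17 (16 settings without rating error), and 1.00–1.38 (8 settings with it). Each figure is uncertain by several per cent.
- *Predicted PASI 75 status* differed between the two models in 8–14% of dropouts without rating error and 4–12% with it. Without rating error, the by-week model classed 1–5 percentage points more dropouts correctly.

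A further check under proportional improvement, with rating error SD 0 to 2 and early or late subject differences, gave a Week 24 SE 7–46% larger under the planned model.

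**Where there is no effect.** Percentage PASI improvement gives 0.99–1.01. A PASI-type check on the NAPSI schedule (Weeks 12 and 24) gives 1.00. DLQI was not simulated.

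**The case against.** The planned MMRM is standard, baseline-adjusted and valid, and the documents set no precision target for Week 24 PASI that it could miss. Every size above rests on assumed slopes and variances. The largest values assume no baseline rating error, although PASI is a physician's ordinal grading and entry is by threshold. With rating error, 85 of 108 settings show a loss of 5% or less. The dropout runs are few and use random dropout, whereas subjects will also leave for adverse events or lack of efficacy. The proposal reaches NAPSI, for which no loss was found, and DLQI, for which none was examined. The PASI 75 prediction may be meant to use the percentage-improvement model, which is unaffected. The statistical analysis plan update may already add the term.

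Most of this stands as a limit on size and reach. It does not remove the point. Rating error alone does not make the loss vanish: the further check included it and still found at least 7%. Which case applies cannot be known before the data are seen, and the term is nearly free when it proves unnecessary. The update is not among the documents, so it cannot be credited with the change.

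**Conclusion.** The concern holds. The plan fits one baseline slope across ten PASI visits, and under plausible conditions this widens the Week 24 interval for PASI score and change. The loss ranges from none, when the slope is constant or subject differences are present early alongside rating error, to 61% in the most adverse setting examined. All of these sizes depend on assumed variances, correlations and slopes.

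With complete data this is a matter of precision, since randomisation keeps the contrast unbiased. With missing-at-random dropout the two models' mean contrasts differed by 0.1 to 0.2 PASI points where the slope changed over time. Percentage improvement and the co-primary tests are not affected. The effect on the supportive PASI 75 prediction is conditional on which model feeds it. The change should be made, but the trial's main conclusion does not depend on it.

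**What to change.** Add a baseline-by-week interaction to the MMRMs in Sections 13.3.6 and 13.3.7, using each endpoint's own baseline value. It matters mainly for absolute PASI and change in PASI; in the other models it is for consistency. Also state which PASI MMRM feeds the PASI 75 prediction in Section 13.3.5. Section 13.3.10 offers a natural place, since "the statistical analysis plan update will be finalised before breaking the randomisation code"; settling the term there avoids choosing a model after the results are known.

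The cost is one term per model. For PASI this means nine further parameters (10 visits − 1) beside 55 covariance parameters (10 × 11/2), and a precision loss under 0.5% if the slope is constant. It is a change of wording, with no new data.
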